3.8 Study Duration and Timeline

Proposed study will be conducted from 1 November 2017- 1 November 2018 in the stages shown below:

- Stage 1, review of medical records – 5 months
- Stage 2, data collection and data analysis –5 months
- Stage 3, presentation and publication – 2 months

3.9 Study Visits and Procedures

No study visits and follow up is required as this is a retrospective study through utilisation of existing patient records for data collection.

3.10 Statistical Analysis Plan

The analyses will be performed using IBM SPSS Statistics for Windows (Version 23.0. Armonk, NY: IBM Corp.). Descriptive statistics will be utilized for selected variables. The results will be presented as frequencies and percentage for Categorical Data. Numerical Data which is normally distributed will be presented as mean and standard deviation while median and interquartile range will be presented for Numerical Data which is not normally distributed.

Comparing Numerical Data which is normally distributed between two groups will be analysed using the Independent t-test while Mann-Whitney test will be used if not normally distributed. Multiple logistic regression will be used to study association between risk factors (Numerical Data/Categorical Data) and outcome (Categorical Data). The survival analyses and survival curves from the date of diagnosis until death will be performed using the Kaplan-Meier method, to estimate the index hospitalisation survival rate. All probability values will be two-sided and a level of significance of less than 0.05 (p-value < 0.05) will be considered as statistically significant.

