Specific Objectives	
• To determine the incidence pattern of Hospital-acquired Acute Kidney Injury in Hospital Selayang• To study the determinants associated with development of Hospital-acquired Acute Kidney Injury in Hospital Selayang• To describe the survival outcomes of admissions with Hospital-acquired Acute Kidney Injury, admissions with Community-acquired Acute Kidney Injury and admissions without Acute Kidney Injury in Hospital Selayang
Study endpoints/outcomes	Completion of data collection at the end of the study duration
Sample Size	170000 (minimum 11345 required)
Study Duration	1 year

1. Background and Significance

Acute kidney injury (AKI) is a common problem globally which imposed heavy illness burden to the healthcare system, especially in developing countries. (1, 2) AKI can occur in the community (termed as Community-acquired AKI (CA-AKI)) or in the hospital setting (termed as Hospital-acquired AKI (HA-AKI)). Studies have associated HA-AKI as a preventable disorder, and linked HA-AKI with several immediate and long-term outcomes adversely, such as length of hospitalization, morbidity, and residual renal function. (1, 3, 4) Moreover, delayed recovery to baseline kidney function after AKI episode is found to be associated with higher risk of adverse events and mortality. (5) The impact of HA-AKI is significantly profound, especially among HA-AKI survivors who lost their residual renal function, and remain dialysis dependent. (6)

There was an increasing trend in HA-AKI incidence among hospitalized patients.(6-8) This could be attributed to increased exposure to potentially preventable risk factors during hospitalization. (6) However, studies pertaining to Asian countries are scarce, especially Malaysia. Preventative strategies against HA-AKI could be formulated based on understanding of risk factors which could be identified earlier upon hospital admission. (4)

The purpose of this study is to compare the incidence trend of HA-AKI in Selayang Hospital for the past 15 years, as well as to determine characteristics predictive of such cases. Understanding of clinical variables associated with HA-AKI could facilitate strategies and approaches to prevent, recognize HA-AKI early and mitigate the disease burden of HA-AKI in future.

2. Objective

2.1 *General Objective*

To investigate the incidence, characteristics and outcomes of Hospital-acquired Acute Kidney Injury in Hospital Selayang over 15 years

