2.2 *Specific Objectives:*

- To determine the incidence pattern of Hospital-acquired Acute Kidney Injury in Hospital Selayang
- To study the determinants associated with development of Hospital-acquired Acute Kidney Injury in Hospital Selayang

- To describe the survival outcome pattern of admissions with Hospital-acquired Acute Kidney Injury, admissions with Community-acquired Acute Kidney Injury and admissions without Acute Kidney Injury in Hospital Selayang

3. Methodology

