3.3 Inclusion Criteria

- a) Age of 18 and above at time of hospital admission
- b) HA-AKI is defined by any patient who developed AKI (as per definition below) after 48 hours of hospital admission.
- c) Definition of AKI(9):

- i. An increase in serum creatinine of 0.3 mg/dl (26.5 μ mol/l) within 48 hours *OR*
- ii. An increase in serum creatinine to more or equal to 1.5 times baseline, which is known or presumed to have occurred within the prior 7 days

d) Definition for baseline creatinine(9):

- i. The baseline creatinine level is defined as the creatinine level at or within 7 days before the hospital admission, *OR*
 - ii. at the hospital admission *OR*
 - iii. the lowest creatinine (excluding the post dialysis creatinine if dialysis is initiated) during the index hospitalisation for those whose baseline creatinine were unknown.

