3.6 Study Outcomes

1. Incidence of Hospital-acquired AKI at our centre during study period
2. Renal recovery at 90 days after AKI diagnosis
Definition for renal recovery:
 - a. Full recovery: Return of serum creatinine to or below baseline or within 20% of baseline creatinine
 - b. Partial recovery: Serum creatinine remaining 20% above the baseline, but below 50% of the baseline and not dialysis dependent or if previously requiring dialysis and now is dialysis Independent.
 - c. Failure to recover: Serum creatinine remains 50% above the baseline or dialysis dependent.
3. In-hospital mortality (from date of AKI diagnosis until date of death in hospital)

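### Objective 3 covers admissions without AKI, but the mortality outcome and survival curves start at AKI diagnosis, and the Kaplan-Meier plan has no rule for live discharge

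*Combined protocol and SAP*

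**What the plan says.** - **Objective.** The synopsis sets out "To describe the survival outcomes of admissions with Hospital-acquired Acute Kidney Injury" and extends this to "admissions with Community-acquired Acute Kidney Injury and admissions without Acute Kidney Injury in Hospital Selayang". Section 2.2 names the same three groups.
- **Mortality outcome.** Section 3.6, outcome 3: "In-hospital mortality (from date of AKI diagnosis until date of death in hospital".
- **Survival analysis.** Section 3.10: "The survival analyses and survival curves from the date of diagnosis until death will be performed using the Kaplan-Meier method", and the stated aim is "to estimate the index hospitalisation survival rate". The sentence names no groups, no censoring rule and no time horizon.
- **General descriptive rule.** Section 3.10: "The results will be presented as frequencies and percentage for Categorical Data".
- **The only follow-up horizon given for an outcome.** Section 3.6, outcome 2: "Renal recovery at 90 days after AKI diagnosis". It applies to renal recovery, not to death.
- **Timing of HA-AKI.** Section 3.3(b): "any patient who developed AKI (as per definition below) after 48 hours of hospital admission".
- **Follow-up.** Section 3.9 requires none; the data come from existing records.

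**The concern.** There are two gaps.

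First, the objective has three groups, but the outcome and the curves both start on a date that only two of them have. Section 3.10 does not say which diagnosis it means. Section 3.6 says AKI, and the plan defines no other diagnosis date. Whoever runs the analysis must therefore choose a start date or a different measure for admissions without AKI after the data are in hand.

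Second, the target is death during one hospital stay, and most stays can be expected to end in live discharge. A Kaplan-Meier analysis needs to know what to do with those patients. If they are censored on leaving, the method treats them as having the same later risk of in-hospital death as patients who stay. A discharged patient can no longer die in that admission, so the curve overstates in-hospital death. If they are instead kept as survivors to a fixed day, it does not. The plan does not say which is meant, and the answer could change the mortality reported for the AKI groups.

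**Working it through.** **1. The plan's own figures.** Section 3.7: 9 predictors × 15 events = 135 events; 135 / 0.0119 = 11,344.5, rounded up to 11,345, as stated. The yearly admissions 22,788 + 41,731 + 46,330 + 59,434 = 170,283, as stated. Neither figure depends on the present point.

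**2. Start date, group by group.**

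| Group in objective 3 | Has an AKI diagnosis date? | 3.6 outcome 3 defined? | 3.10 curve defined? |
|---|---|---|---|
| HA-AKI | yes | yes | start yes; discharge rule and horizon no |
| CA-AKI | yes | yes | start yes; discharge rule and horizon no |
| No AKI | no | no | no |

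**3. Scale for precision.** If the 1.19% in section 3.7 held for every year, there would be 170,283 × 0.0119 = 2,026 HA-AKI admissions, and 22,788 × 0.0119 = 271 in the 2002 cohort. This is an assumption: the rate comes from March 2017, and the totals are before the renal failure exclusion.

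**4. Size of the discharge effect.** All inputs here are assumed. Let p be the risk of dying in hospital, m the mean stay in days, and let the hazards of death and discharge be constant. The death hazard is then p/m.

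- True in-hospital death by day t: p × (1 − exp(−t/m)).
- One minus Kaplan-Meier with discharge censored: 1 − exp(−p·t/m).

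Over p = 1, 5, 10, 20, 30% and m = 5, 10, 15 days, the ratio of the second to the first is:

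| | Smallest (p = 30%, m = 15) | Largest (p = 1%, m = 5) |
|---|---|---|
| Day 7 | 13.06% / 11.19% = 1.17 | 1.390% / 0.753% = 1.85 |
| Day 14 | 24.42% / 18.20% = 1.34 | 2.761% / 0.939% = 2.94 |

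The excess depends on length of stay. At day 7 with p = 10%:

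| Mean stay | True | 1 − KM | Excess (points) |
|---|---|---|---|
| 5 days | 7.53% | 13.06% | 5.5 |
| 10 days | 5.03% | 6.76% | 1.7 |
| 15 days | 3.73% | 4.56% | 0.8 |

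**5. Comparison with sampling error.** The Greenwood 95% half-width under the same model is 1.96 × exp(−p·t/m) × √[(p/n)(exp(t/m) − 1)].

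- p = 20%, m = 10, day 14: true 15.1%, one minus Kaplan-Meier 24.4%, excess 9.4 points. With n = 2,026 the half-width is 1.96 × 0.7558 × √(0.2 × 3.055 / 2,026) = 2.6 points; with n = 271 it is 7.0. The excess is larger than both.
- p = 10%, m = 15, day 7: excess 0.8 points against 1.0 with n = 2,026. Within sampling error.
- p = 10%, m = 10, day 7: excess 1.7 points against 3.5 with n = 271. Within sampling error.

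**The case against.** The strongest reply is that objective 3 only describes. The Kaplan-Meier sentence names no groups, its start date naturally limits it to AKI admissions, and the plan promises no curve or test for admissions without AKI. Percentages under the general rule in 3.10 would cover died or alive in that group. This stands in part: a reader might infer that survival without AKI cannot be described at all, and the documents do not support that. What remains is that the only mortality outcome in the plan, 3.6 outcome 3, is not worded for that group.

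A second reply is that the wording of 3.6 and 3.10 already confines follow-up to the stay. That is true, but it does not say how live discharge is coded, and the coding determines the estimate.

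A third reply is that the size of any bias in this study is unknown, because every mortality and length-of-stay figure above is assumed. That also stands. A reader might infer that the bias must exceed sampling error; two of the three cases in step 5 show otherwise. A reader might also infer that admissions without AKI are most of the cohort. Section 3.7 gives only the HA-AKI rate and no CA-AKI share, so that cannot be derived.

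Finally, Figure 1, the study flow chart, is not shown in the text available and could not be checked.

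**Conclusion.** Both gaps are real. The wording of 3.6 outcome 3 and of 3.10 supplies no start date for one of the three groups in objective 3, and 3.10 estimates an in-hospital rate by Kaplan-Meier with no rule for live discharge and no horizon. The first follows from the text alone and needs no assumption.

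The size of the second is conditional on discharge being censored and on the assumed constant hazards. Then in-hospital death is overstated by a factor of 1.2–1.8 at day 7 and 1.3–2.9 at day 14. That can be well beyond sampling error (9.4 points against 2.6) or inside it (0.8 against 1.0).

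The consequence is limited to descriptive objective 3. Incidence, the determinants analysis and the sample size are unaffected. It should be fixed before the analysis, because the omitted choices would otherwise be made with the results in view.

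**What to change.** **(a) Section 3.6, outcome 3.** Define in-hospital mortality as death before discharge from the index admission, so that it exists for all three groups. Report the proportion with a 95% confidence interval in each group. Restrict any comparison that includes HA-AKI to admissions still in hospital at 48 hours: HA-AKI can only be diagnosed after that time, so deaths and discharges in the first 48 hours can fall only in the other groups.

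**(b) Section 3.10.** Limit curves from AKI diagnosis to HA-AKI and CA-AKI. Show the cumulative incidence of in-hospital death, with live discharge as a competing event, to a stated horizon. Kaplan-Meier with discharged patients held as survivors to that horizon gives the same curve, provided nobody is censored earlier for another reason, and can be run in SPSS, which 3.10 already names.

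**Cost.** A change of wording in two sections and slightly more analysis, with no new patients. The team should confirm that admission date, discharge date and vital status at discharge are extracted for admissions without AKI; objective 3 needs these in any case.

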3.11 Risk and benefit to study participants

As this is a retrospective data collection of the participants, no intervention, procedure or treatment will be imposed to the participants during the whole course of the study. Thus, there is minimal risk to the participants.

Benefits to the participants

This study does not present any direct benefit to the participants. However, understanding of HA-AKI patterns at our centre will help in formulating preventative strategies related with HA-AKI.

3.12 Risk Benefit Assessment

As stated above, there is no risk from this study. Study findings shall potentially greatly improve treatment outcomes. The expected benefit outweighs the minimal risk to subjects and thus this study should be supported.

3.13 Ethics of Study

Study will be conducted in compliance with ethical principles outlined in the Declaration of Helsinki and Malaysian Good Clinical Practice Guideline.

3.14 Informed Consent/Assent Process

Not applicable. Consent waiver is permitted from Medical Research Ethics Committee, Ministry of Health Malaysia for this retrospective study and there are no additional study procedures/visits pertaining to this study. Participants' data will be de-identified as there is no collection of personal, identifiable data.

3.15 Privacy and Confidentiality

Subject's names will be kept on a password-protected database and will be linked only with a study identification number for this research. The identification number instead of patient identifiers will be used on subject data sheets. All data will be entered into a computer that is password protected. On completion of study, data in the computer will be copied to CDs and the data in the computer erased. CDs and any hardcopy data will be stored in a locked office of the investigators and maintained for a minimum of three years after the completion of the study. The CDs and data will be destroyed after that period of storage. Subjects will not be allowed to view their personal study data, as the data will be consolidated into a database.

3.16 Conflict of Interest

The investigators declare they have no conflict of interest.

3.17 Publication Policy

No personal information will be disclosed and subjects will not be identified when the findings of the survey are published.

